### 3.2.2. Secondary Endpoints

#### Immunogenicity

- 50% neutralizing antibody (NT50) geometric mean titer (GMT) against SARS-CoV-2 pseudovirus at baseline, 28 days after the first vaccination and 14 days and 6 months after the second vaccination in all the subjects. The primary analysis will be conducted separately for those who are anti-S IgG seronegative at baseline (no pre-screening for SARS-CoV-2 will be carried out)
- Geometric mean fold rise (GMFR) (from baseline) in NT50 against SARS-CoV-2 pseudovirus at 28 days after the first vaccination, and 14 days and 6 months after the second vaccination
- Percentage of subjects with NT50 seroresponses against SARS-CoV-2 pseudovirus as defined by (1) a  $\geq 4$ -fold increase from baseline, and (2) a  $\geq 10$ -fold increase from baseline at 28 days after the first vaccination and 14 days and 6 months after the second vaccination
- Anti-S IgG GMT at baseline and at 28 days after the first vaccination and 14 days and 6 months after the second vaccination
- GMFR (from baseline) in anti-S IgG GMT at 28 days after the first vaccination and 14 days and 6 months after the second vaccination
- Percentage of subjects with seroresponses in anti-S IgG titer as defined by (1) a  $\geq 4$ -fold increase from baseline, and (2) a  $\geq 10$ -fold increase from baseline, at

28 days after the first vaccination and 14 days and 6 months after the second vaccination

### **3.2.3. Exploratory Endpoint:**

- Anti-NDV HN IgG GMT at baseline, 28 days after the first vaccination, and 14 days and 6 months after the second vaccination
- 80% neutralization antibody (NT80) GMT, GMFR and percentage of seroresponders ( $\geq$  4-fold increase from baseline)

## **3.3. Study Definitions and Derived Variables**

### **3.3.1. Adverse Event**

An adverse event is any untoward, undesired, or unplanned event in the form of signs, symptoms, disease, or laboratory or psychological/physiologic observations occurring in a subject enrolled in the clinical trial. This includes all subjects from whom consent has been obtained whether or not they have yet been randomized and received a study product. The event does not need to be causally related to trial participation or receipt of a study product. An AE is temporally related to participation in the study and will be documented as to whether or not it is considered to be related to vaccine. An AE includes, but is not limited to, the following:

- An intercurrent illness or injury during the course of the study
- Any clinically significant worsening of a preexisting condition

### **3.3.2. Solicited Adverse Event**

Solicited adverse events are pre-specified injection-site-specific local and systemic AEs that occur relatively more frequently, or are known to be associated with, immunization, and which are monitored actively as potential indicators of vaccine reactogenicity. Investigators will not be required to assess causality of solicited AEs if the onset is during the solicitation period.

The following specific solicited AEs will be monitored for this study:

Local solicited AEs assessed at the injection site:

- Pain or tenderness
- Swelling or induration
- Erythema

Systemic solicited AEs:

- Fever (defined as oral temperature  $\geq 38^{\circ}\text{C}$ )
- Headache
- Fatigue or malaise
- Myalgia
- Arthralgia

- Nausea or vomiting

### **3.3.3. Unsolicited Adverse Event**

An unsolicited adverse event is any AE reported spontaneously by the subject, observed by the study staff during study visits or those identified during review of medical records or source documents. Solicited AEs with an onset after the seven-day solicitation period will be considered unsolicited AEs. In the absence of a diagnosis, abnormal physical examination findings or abnormal clinical safety laboratory test results that are assessed by the investigator to be clinically significant will be recorded as an AE.

### **3.3.4. Medically-Attended Adverse Event**

A medically-attended adverse event is an unsolicited AE for which the subject received medical attention, such as during an emergency room visit or a visit to or from medical personnel (e.g., medical doctor).

### **3.3.5. Adverse Event of Special Interest**

An adverse event of special interest (AESI) is an AE of scientific and medical concern specific to the Sponsor's product or program, for which ongoing monitoring and rapid communication by the investigator to the Sponsor can be appropriate. Such an event might warrant further investigation in order to characterize and understand it.

The AESI to be monitored in this study include the following:

- Potential immune-mediated medical conditions (PIMMC), given that vaccination has been associated with autoimmunity
- AEs associated with COVID-19, given the importance to subject safety of managing any occurrence of COVID-19, and the possible association of vaccination with enhancement of COVID-19

### **3.3.6. Protocol-Related Adverse Event**

A protocol-related adverse event is an AE that occurs from the time of enrollment until the EOS visit that is not considered to be related to receipt of the study vaccine, but is considered by the PI/designee or the Sponsor to be related to the research conditions, i.e., related to the fact that a subject is participating in the study. For example, a protocol-related AE may be an untoward event occurring during blood sampling or other protocol-specified activity.

### **3.3.7. Treatment-Emergent Adverse Event**

A treatment-emergent AE is defined as an AE that is not present prior to administration of the study product, or, if present prior to the administration of the study medication, increases in intensity after administration of the study medication during the course of the study.

### **3.3.8. Serious Adverse Event**

An SAE is a specific AE that:

- Results in death.

- Is life-threatening.\*
- Requires inpatient hospitalization or prolongation of an existing hospitalization.\*\*
- Results in a persistent or significant disability or incapacity.\*\*\*
- Results in a congenital anomaly or birth defect.

\***Life-threatening** refers to immediate risk of death as the event occurred per the reporter. A life-threatening event does not include an event that, had it occurred in a more severe form, might have caused death but, as it actually occurred, did not create an immediate risk of death.

For example, hepatitis that resolved without evidence of hepatic failure would not be considered life-threatening, even though hepatitis of a more severe nature can be fatal. Similarly, an allergic reaction resulting in angioedema of the face would not be life-threatening, even though angioedema of the larynx, allergic bronchospasm, or anaphylaxis can be fatal.

\*\***Hospitalization** is an admission to a health facility in the situation where there is an AE. A period of observation at a clinical trial site is not considered to represent hospitalization for the purposes of SAE reporting. Hospitalization or prolongation of a hospitalization constitutes a criterion for an AE to be serious; however, it is not in itself considered an SAE. In absence of an AE, a hospitalization or prolongation of a hospitalization should not be reported as an SAE by the PI/designee on a SAE form. Such situations include, but are not limited to, the following:

- A hospitalization for a preexisting condition that has not worsened.
- Hospitalization for social reasons.

\*\*\***Disability** is defined as a substantial disruption in a person's ability to conduct normal life functions. If there is any doubt about whether the information constitutes an SAE, the information is treated as an SAE.

Medical and scientific judgment should be exercised in deciding whether expedited reporting is appropriate in other situations, such as **important medical events** that may not be immediately life-threatening or result in death or hospitalization but may jeopardize the patient or may require intervention to prevent one of the other outcomes listed in the definition above. These should also usually be considered serious. Examples of such events are intensive treatment in an emergency room or at home for allergic bronchospasm, or blood dyscrasias or convulsions that do not result in hospitalization.

### 3.3.9. Severity (Intensity) of Adverse Event

The severity of all solicited AEs will be graded from Mild (Grade 1) to Potentially Life Threatening (Grade 4). All AEs leading to death are Grade 5 events. Adverse events are graded based on the worst severity grade during the illness/symptoms. All other unsolicited AEs will be classified as an AE and graded based on the AE severity scale in table of severity grading below. The grading scales for solicited and unsolicited AEs have been derived from the *Division of AIDS (DAIDS) Table for Grading the Severity of Adult and Pediatric Adverse Events* (Version 2.1, July 2017), from the US National Institutes of Health.

**Table of Severity Grading – Protocol Table 6**

Grade	Description
1	Causes no or minimal interference with normal daily activities; intervention not indicated
2	Interferes with but does not prevent normal daily activities; intervention indicated
3	Prevents normal daily activities; intervention or hospitalization indicated
4	Causes inability to perform basic self-care activities; intervention indicated to prevent permanent impairment, persistent disability, or death

**3.3.10. Causal Relationship of an Adverse Event**

A suspected adverse drug reaction (ADR) means any AE for which there is a reasonable possibility that the study vaccine caused the AE. A reasonable possibility means there is evidence to suggest a causal relationship between the vaccine and the AE. All cases judged by either the PI/designee or the Sponsor as having a reasonable suspected causal relationship to the study vaccine will qualify as ADRs. Medical judgment will be used to determine the relationship, considering all relevant factors, including pattern of reaction, temporal relationship, confounding factors such as concomitant medication, concomitant diseases, and relevant history.

The likelihood of the relationship of the AE to study vaccine is to be recorded as follows:

- Related: There is a reasonable causal relationship between the vaccine administered and the AE.
- Not Related: There is no reasonable causal relationship between the vaccine administered and the AE.

Note: solicited reactogenicity events will not be judged for relatedness.

**3.3.11. Assessment of Outcome of Adverse Event**

The outcome of the AE will be assessed and recorded as per the following categories:

- Ongoing
- Recovered/resolved
- Recovered/resolved with sequelae
- Fatal
- Unknown

**3.3.12. Adverse Event Recording and Reporting**

Recording and reporting of all AEs will occur from signing of the ICF (enrollment) through 28 days post-second injection (Visit 6) for each study subject receiving study product. SAEs, MAAEs, and AESI will be recorded throughout the study period. The Study staff must completely and promptly record each AE in the source documentation and on the AE CRF,

regardless of relationship to the vaccine administered/procedure as determined by the PI/designee. The PI/designee will attempt, if possible, to establish a diagnosis based on the signs and symptoms. When a diagnosis for the reported signs or symptoms is known, the PI/designee will report the diagnosis as the AE, not the signs and symptoms. Adverse events will be classified by MedDRA term and by severity/intensity, relatedness, and outcome.

Enrolled subjects who subsequently screen fail (i.e., who never underwent randomization) will have any AEs recorded from enrollment until the time they are determined to be ineligible for randomization or withdraw consent. These AEs will be listed in separate appendices from those subjects randomized and vaccinated. For the purposes of data capture they will be closed at the point the subject is deemed ineligible.

Reporting of AEs will follow the regulatory guidelines of the Ministry of Health and NIHE's Ethics Committee (EC) in regard to requirements, processes and forms.

### **3.3.13.        Serious Adverse Event Reporting**

If an AE is classified as serious, an SAE form will be completed and submitted within 24 hours of the PI/designee becoming aware of the SAE, including information on the location, severity, relatedness, and clinical summary of the event to the Sponsor to initiate any PSRT evaluation and any additional reporting requirements. In addition, the SAE submission will follow the regulatory guidelines of the Ministry of Health and NIHE's IRB in regards to requirements, processes and forms. It is the responsibility of the Sponsor to ensure that Dynavax Technologies Corporation (manufacturer of the adjuvant CpG 1018) and the other Consortium manufacturers are notified of SAEs and other notable safety events per agreed procedures and timelines. Any SAE deemed related to study vaccine that is ongoing at the time of last subject last visit (LSLV) will continue to be followed until it is resolved, assessed to be resolved with sequelae, or assessed to be stable/chronic. SAEs deemed not related to study vaccine that are unresolved at the time of LSLV will be classified as ongoing.

### **3.3.14.        Unanticipated Problems**

All unanticipated problems will be reported in the continuing review report submitted to the Ministry of Health and NIHE's IRB per reporting requirements of each regulatory body. All serious unanticipated problems involving risk to participants or others will be promptly (within 48 hours) reported by telephone, by email, or by facsimile to the Sponsor. Follow-up reports will be submitted as soon as additional information becomes available.

## **4.                INVESTIGATIONAL PLAN**

[figure not shown]
### **4.1.              Overall Study Design and Plan**

This prospective, single-center, randomized, placebo-controlled, observer-blind Phase 1/2 study includes two separate parts. The treatment groups to be evaluated in each part of the study (and their corresponding sample size) are presented in Table 1.

**Table 1: Treatment Groups - Protocol Table 3**

Group	Sample Size	Study Product
1	20	Placebo
2	25	NDV-HXP-S 1 µg
3	25	NDV-HXP-S 3 µg
4	25	NDV-HXP-S 10 µg
5	25	NDV-HXP-S 1 µg + CpG1018 1.5 mg

Phase 1 study designed to evaluate the safety, tolerability, and immunogenicity of the NDV-HXP-S vaccine at three different dose levels (1, 3, and 10 µg) without adjuvant, and at one dose level (1 µg) with the adjuvant CpG 1018, in a total of 120 subjects aged 18-59 years. Eligible subjects will be randomly assigned to receive study vaccine or placebo as an IM injection in the deltoid muscle at Visit [V]1 as part of one of four sequential groups of escalating antigen dose level or added adjuvant. Each group will be divided into two sequential subgroups, a sentinel subgroup (n=6) and a larger subgroup (n=24) that includes the remaining subjects to be evaluated at that dose level (or for that formulation in the case of the one adjuvanted treatment group). Initially, a sentinel subgroup of 6 subjects will be randomized to receive NDV-HXP-S 1 µg or placebo in a 5:1 ratio (subjects within a sentinel subgroup will receive the first injection only after immediate reactogenicity assessments of the prior subject in the subgroup are completed). Sentinel subjects will be monitored for reactogenicity and safety through Day 8 (Visit 2), including for the initial 24 hours post-injection in clinic. If the PSRT has no safety concerns based on blinded review of all safety data, including clinical laboratory results, through Visit 2, the second subgroup of 24 subjects will be randomized to receive NDV-HXP-S 1 µg or placebo at the same ratio; on the same day, the sentinel subgroup (n=6) for the second dose level to be evaluated (NDV-HXP-S 3 µg) can be randomized to receive study vaccine or placebo in a 5:1 ratio, and so on for the subsequent dose level and formulation (see Table 2).

**Table 2: Phase 1 Dose Escalation Steps – Protocol Table 4**

V1 = Visit 1 (Day 1)

V2 = Visit 2 (Day 8)

PSRT = Protocol Safety Review Team meeting

The PSRT will review blinded safety, reactogenicity and clinical laboratory data accrued on a weekly basis until D43 of the last subject in each phase of the study, then at least once monthly until the end of the study. Subjects will receive 2 doses of assigned IP on D1 and D29 (V1 and V3), and be assessed in clinic for safety and reactogenicity at 7 days after each vaccination (V2 and V4), for safety at 28 days after the second vaccination (V6), and for safety and immunogenicity assessments at baseline (V1), 28 days after the first vaccination (V3) and 14, 168 and 336 days after the second vaccination (V5, V7, and V8, EOS Visit).

An interim analysis of Phase 1 data conducted after the last subject last visit for V6 (D57) will serve as the basis for decisions about down-selection and advancing to Part 2 of the study (Phase 2). Down selection and advancement to Part 2 (Phase 2) will be based on the following parameters:

- Post-dose 2 immunogenicity results at the aggregate treatment level
  - A threshold immune response at Day 43 will be required: the observed seroresponse rate in a treatment group (defined as the percentage of subjects with at least a 4-fold rise from baseline in 80% neutralizing antibody titers) will need to be  $\geq 52\%$  at the LL of the 95% CI for that treatment (vaccine formulation) to be considered for advancement to Phase 2.
- Post-dose 1 and post-dose 2 safety results including all solicited and unsolicited adverse events, serious adverse events, and clinical laboratory results.

The following process will be followed for the decision about down-selection and advancing Part 2 (Phase 2):

- The DSMB will review the unblinded safety data and provide a recommendation to the Sponsor on whether the safety profile is acceptable for advancing a formulation to Phase 2.
- The Sponsor will review the DSMB recommendation in conjunction with the immunogenicity data and select two formulations to advance to Phase 2.
  - If multiple formulations achieve the threshold immune response (as well as have an adequate safety and tolerability profile per the DSMB), the Sponsor will select two formulations to advance to Phase 2 based on consideration of such factors as the relative functional immunogenicity of these formulations, opportunity for dose sparing, and opportunity to limit cost and possible supply constraints associated with use of the CpG adjuvant.
- The selection and recommendation to advance to Phase 2 along with the interim report will be jointly reviewed by NIHE's IRB and MoH prior to Phase 2 enrollment.

## 4.2. Selection of Study Population

### 4.2.1. Description of Study Population

For Phase 1, the study population will consist of eligible, Vietnamese male and female adults aged 18-59 years old, inclusive.

### 4.2.2. Inclusion Criteria for Enrollment

Participants are eligible for Phase 1 study if they fulfill the inclusion criteria below:

- Adult 18 through 59 years of age inclusive at the time of randomization.
- Healthy, as defined by absence of clinically significant medical condition, either acute or chronic, as determined by medical history, physical examination, screening laboratory test results, and clinical assessment of the investigator.
- Has provided written informed consent prior to performance of any study-specific procedure.
- Has a body mass index (BMI) of 17 to 40 kg/m^2, inclusive, at screening.
- Resides in study site area and is able and willing to adhere to all protocol visits and procedures.
- If a woman is of childbearing potential, must not be breastfeeding or be pregnant (based on a negative urine pregnancy test at screening and during the 24 hours prior to receipt of the first dose of IP), must plan to avoid pregnancy for at least 28 days after the last dose of IP, and be willing to use an adequate method of contraception consistently and have a repeated pregnancy test prior to the second (last) dose of IP.

### 4.2.3. Exclusion Criteria for Enrollment

Participants will be ineligible for this study for any of the following conditions or reasons:

- Use of any investigational medicinal product within 90 days prior to randomization or planned use of such a product during the period of study participation.
- History of administration of any non-study vaccine within 28 days prior to administration of study vaccine or planned within 3 months after enrolment.

**Note:** receipt of any COVID-19 vaccine that is licensed or granted Emergency Use Authorization in Vietnam during the course of study participation is not exclusionary if administered after Visit 5.

- Previous receipt of investigational vaccine for SARS or MERS, or any investigational or licensed vaccine that may have an impact on interpretation of the trial results.
- History of hypersensitivity reaction to any prior vaccination or known hypersensitivity to any component of the study vaccine.
- History of egg or chicken allergy.
- History of angioedema.
- History of anaphylaxis.
- Acute illness (moderate or severe) and/or fever (body temperature measured orally  $\geq 38^{\circ}\text{C}$ ).
- Any abnormal vital sign deemed clinically relevant by the PI.
- Abnormality in screening laboratory test deemed exclusionary by the PI in consultation with the Sponsor.
- A positive serologic test for hepatitis B (HBsAg) or hepatitis C (HCV Ab).
- History of laboratory-confirmed COVID-19 (RT-PCR positive to SARS-CoV-2).
- History of confirmed HIV.
- History of laboratory-confirmed COVID-19.
- History of malignancy, excluding non-melanoma skin and cervical carcinoma in situ.
- Any confirmed or suspected immunosuppressive or immunodeficient state.
- Administration of immunoglobulin or any blood product within 90 days prior to first study injection or planned administration during the study period.
- Administration of any long-acting immune-modifying drugs (e.g., infliximab or rituximab) or the chronic administration (defined as more than 14 days) of immunosuppressants within six months prior to first study injection, or planned administration during the study period (includes systemic corticosteroids at doses equivalent to  $\geq 0.5$  mg/kg/day of prednisone; the use of topical steroids including inhaled and intranasal steroids is permitted).
- History of known disturbance of coagulation or blood disorder that could cause anemia or excess bleeding (e.g, thalassemia, coagulation factor deficiencies).
- Recent history (within the past year) or signs of alcohol or substance abuse.
- Any medical, psychiatric or behavior condition that in the opinion of the PI may interfere with the study objectives, pose a risk to the subject, or prevent the subject from completing the study follow- up.
- Employee of any person employed by the Sponsor, the contract research organization (CRO), the PI, study site personnel, or site.

**Note:** specific exclusion criteria (e.g.,  $\geq$  Grade 2 acute illness, or abnormal vital sign deemed clinically relevant by the PI/designee) will be reassessed at both vaccination visits. Any subject who cannot be vaccinated due to an acute abnormality assessed at a vaccination visit (Visit 1 or Visit 3) may return once the acute issue has resolved, if deemed appropriate by the PI/designee. A minimum of 48 hours must have passed after a documented fever before a subject can be vaccinated. This safety requirement will not be deemed a protocol deviation should the visit fall outside the vaccination window; however, it will be encouraged to maintain the vaccination window whenever possible in these situations. Clinical laboratory test results and vital signs used to determine subject eligibility will be those obtained at screening. These tests may be repeated once if deemed appropriate by the investigator and determined to be due to a transient condition that has resolved. In addition, a test may also be repeated for test results determined to be spurious by the investigator (e.g., following improper specimen collection). The last measurement will be taken as the baseline for purposes of analysis.

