#### **4.6. Prior and Concomitant Therapy**

All concomitant medications will be recorded in source documents from Visit 1 (Day 1) through Visit 6 (Day 57). After Visit 6, only those concomitant medications associated with AESI, MAAEs, and SAEs will be recorded. Details on concomitant medications to be recorded include the generic and/or trade name, indication, dosage, regimen, route of administration, and start and end dates of the medication.

The following concomitant medications are prohibited during the study; however, they must not be withheld by the treating physician if clinically indicated to treat a subject:

- Any investigational medicinal product other than the study product
- Administration of immunoglobulins or any blood products
- Administration of any long-acting immune-modifying drugs (e.g., infliximab or rituximab) or the chronic administration (defined as more than 14 days) of immunosuppressive medications (includes systemic corticosteroids at doses equivalent to  $\geq 0.5$  mg/kg/day of prednisone; the use of topical steroids including inhaled and intranasal steroids is permitted).

Use of any prohibited medication must be recorded in the CRF. Whether a subject who uses a prohibited medication will be included in the Per Protocol Population will be evaluated on a case by case basis.

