#### **6.3.4. Full Analysis Population**

All subjects in the exposed population for whom any post-study product administration immunogenicity results are available. An immunogenicity analysis will also be performed using this population.

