#### **6.3.5. Per Protocol Population**

All subjects in the exposed population who have no major protocol deviations that are determined to potentially interfere with the immunogenicity assessment of the study product.

This population will serve as the primary analysis population for the immunogenicity endpoints. The population will be adapted by time point to include all eligible subjects' data up to the time of disqualifying protocol deviation. The criteria (e.g., intake of prohibited medication expected to influence the immune response) for exclusion of subjects from the per protocol population, and determination of any exclusions based on a blinded review of the data, will be established before database freeze and lock for both interim and final analyses, respectively.

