**Table 1: Treatment Groups - Protocol Table 3 (see [Table 1](#) in Section [4.1.](#))**

**Table 2: Phase 1 Dose Escalation Step – Protocol Table 4 (see [Table 2](#) in Section [4.1.](#))**

**Table 3: Schedule of Study Visits and Procedures – Protocol Table 5**

VISIT	Screen	V1	V2	V3	V4	V5	V6	V7
Study Day (allowed window in days)	-42 to 1	1	8 (+3)	29 (+3)	36 (+3)	43 (+3)	57 (+7)	197 (+14)
Informed consent	✓							
Demographics	✓							
Medical History	✓							
Concomitant medications A	✓	✓	✓	✓	✓	✓	✓	✓
Eligibility check	✓			~				
Vital signs	✓	✓ ^ ✓	✓	✓ ^ ✓	✓	✓	✓	✓
Complete physical exam	✓							
Targeted physical exam B		✓	✓	✓	✓	✓	✓	✓
Clinical chemistry C	✓		✓		✓			
Hematology D	✓		✓		✓			
Viral serology tests E	✓							
Urine pregnancy test F	✓	✓ ^ ✓		✓				
Unsolicited AEs G	✓	✓	✓	✓	✓	✓	✓	✓
Concomitant medications H	✓		✓	✓	✓	✓	✓	✓
Randomization		✓		~				
Blood for humoral immunity		✓		✓		✓		✓
Blood for CMI I		✓				✓		✓
Administer study product		✓		✓				
Observation/solicited AEs		✓		✓				
Provide Diary Card		✓		✓				
Review Diary Card			✓		✓			
Exit study								
Blood volumes (mL):								
Safety laboratory tests (Phase 1 only)	4		4		4			
HBV and HCV screening	2		0		0			
Humoral immunity		10		10		10		10
Cell-mediated immunity		16				16		16

~ Confirmation

A Evaluations will be conducted twice – before and after vaccinationB After Visit 6, only medications associated with an AESI, MAAE or SAE will be recorded.C Targeted PE will be conducted only in the event of new symptom, sign or, until Visit 6, any new AE; or, after Visit 6, any new AESI, MAAE or SAE.D Serum creatinine, ALT, AST, total bilirubin; only in Phase 1.E WBC count, hemoglobin, platelets; only in Phase 1.F HBsAg, HCV AbG Women of childbearing potential (WOCBP) onlyH After Visit 6, only AESI, MAAEs, and SAEs will be recorded.I After Visit 6, only concomitant medications associated with a newly reported AESI, MAAE or SAE will be recorded Only in subset of subjects in Phase 2

Remark: 1 month = 28 days (4 weeks)

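### Day 197 antibody results can include responses to other COVID-19 vaccines: these are permitted after Visit 5, not routinely recorded after Visit 6, and covered by no analysis rule

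*SAP*

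**What the plan says.** **Permission.** Section 4.2.3 makes one group ineligible: "History of administration of any non-study vaccine within 28 days prior to administration of study vaccine or planned within 3 months after enrolment". A note beneath it carves out COVID-19 vaccines, saying that one which is licensed or "granted Emergency Use Authorization in Vietnam during the course of study participation is not exclusionary if administered after Visit 5". Visit 5 is Day 43.

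**Prohibited list.** Section 4.6 names "Any investigational medicinal product other than the study product", immunoglobulins and blood products, and immune-modifying or immunosuppressive drugs. Licensed or emergency-authorised vaccines are not on it.

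**Recording.** Section 4.6 has all concomitant medication recorded from Day 1 to Day 57. Then: "After Visit 6, only those concomitant medications associated with AESI, MAAEs, and SAEs will be recorded". A footnote to Table 3 repeats the limit: "After Visit 6, only medications associated with an AESI, MAAE or SAE will be recorded".

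**Analysis sets.** The per protocol population (6.3.5), which is primary for immunogenicity, is "All subjects in the exposed population who have no major protocol deviations that are determined to potentially interfere with the immunogenicity assessment". It is adapted by time point, and a subject's data count up to the disqualifying deviation. Section 4.8 defines a deviation as noncompliance. The full analysis population (6.3.4) is "All subjects in the exposed population for whom any post-study product administration immunogenicity results are available".

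**Endpoints.** Section 3.2.2 lists NT50 and anti-S IgG GMT, GMFR and seroresponse at 6 months after dose 2 as secondary endpoints. NT80 is exploratory (3.2.3).

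**The concern.** The Day 197 results are meant to describe persistence of the response to NDV-HXP-S. Section 9.2 says the ELISA detects IgG to the full-length Spike protein, and the assay in 9.1 measures neutralization of a SARS-CoV-2 pseudovirus. Neither separates the study vaccine from another Spike-based vaccine given after Day 43.

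Read together, the permission, the recording limit and the deviation-only cut-off mean that such samples stay in both analysis sets and mostly cannot be identified. Waning could be masked, placebo recipients could count as seroresponders, and differences between formulations could be blurred. Section 4.2.3 itself excludes prior receipt of vaccines that could affect interpretation of the results, so the plan accepts the principle but has no rule for use during follow-up.

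**Working it through.** **1. The plan's own figure.** The SAP gives no figure for this problem. The nearest is the Day 43 selection rule in section 5: exact 95% lower limit of at least 52%, with 90% power at a true rate of 85%. It reproduces. With n = 22, 17 responders are needed (lower limit 54.6%) and power is 90.0%; with n = 25, 19 are needed (54.9%) and power is 93.0%. Other vaccines are allowed only after the Day 43 visit, so this rule is untouched.

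**2. Following one vaccination through the plan.** Take a subject given an authorised COVID-19 vaccine on Day 100.
- 4.2.3 allows it, 4.6 does not prohibit it, and under 4.8 it is not noncompliance.
- 4.6 and Table 3 do not record it unless it is tied to an AESI, MAAE or SAE.
- 6.3.5 has no deviation at which to cut the data; 6.3.4 has no exclusion.
- Section 9 restricts GMTs by baseline serostatus only. Section 6.4 uses no covariates, and 6.5 addresses missing data only.
- Table 16 covers vaccination in the past year. No table or listing covers a non-study COVID-19 vaccine given during the study.

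**3. Length of the unrecorded window (nominal days).** Permitted: 197 − 43 = 154 days. Not routinely recorded: 197 − 57 = 140 days. 140/154 = 91%.

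**4. Possible size.** Uptake f between Day 43 and Day 197, and the titre multiplier r in recipients, are not in the SAP. Both are assumed: f from 25% to 80%, r of 4 or 10.
- Group GMT is multiplied by r^f.
- A seroresponse rate p becomes p + f(1 − p) if every recipient responds.
- A true between-group GMT ratio of 2 becomes 2^(1 − f) if uptake is equal in both groups and recipients reach a common level.

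| f | GMT factor, r = 4 | GMT factor, r = 10 | Placebo 4-fold rate, truly 0% | Ratio of 2 becomes |
|---|---|---|---|---|
| 25% | 1.41 | 1.78 | 25% | 1.68 |
| 50% | 2.00 | 3.16 | 50% | 1.41 |
| 80% | 3.03 | 6.31 | 80% | 1.15 |

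If uptake differs between groups, the ratio is also shifted by r raised to the difference. A 30-point difference gives 4^0.3 = 1.52 or 10^0.3 = 2.0.

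**5. Price of excluding affected samples.** Section 5 assumes 22 evaluable subjects per candidate group and a log10 variability of 0.5, taken here as the SD and carried over to Day 197. The 95% limits are the GMT multiplied and divided by 10^(t × 0.5/√n), with t the 97.5% point on n − 1 degrees of freedom. With n = 22 the factor is 1.67. At uptake of 25%, 50% and 80%, n falls to about 16, 11 and 4, and the factor becomes 1.85, 2.17 and 6.25.

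**The case against.** Several counter-arguments have force.

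- **COVID-19 illness is already captured.** COVID-19-associated events are AESIs (3.3.5), recorded throughout (3.3.12) and through Day 197 (8.3.2), with Table 47 and dated entries in Listing 7. This stands. For symptomatic infection the gap is a missing analysis rule, not missing data.
- **Vaccines given between Visits 5 and 6 are recorded.** This stands. The recording gap starts at Day 57.
- **The per protocol criteria are not closed.** Section 6.3.5 leaves them to be settled before lock, gives prohibited medication only as an example, and Table 7 has exclusion rows for D197. This stands in part. The route is still tied to deviations, and a criterion added later could not be applied reliably without vaccination dates.
- **The non-deviation status is inferred.** No sentence says it outright, but it follows from the note in 4.2.3, the list in 4.6 and the definition in 4.8.
- **The protocol or CRF may capture these vaccines.** That cannot be ruled out. This SAP states the recording limit twice and plans no use of such data.
- **Nothing decisive rests on Day 197.** Safety is primary, and formulations are selected on Day 43 immunogenicity and safety to Day 57. This stands and limits the severity.
- **Exclusion has its own bias.** Those who remain have selected themselves after randomisation. This stands, and is the reason to show results both ways.

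**Conclusion.** The point holds and should be fixed. Followed as written, the plan can attribute other vaccines' anti-S and neutralizing responses at Day 197 to NDV-HXP-S, with no reliable means of detecting it. The 12-month time point that 9.1 and 9.2 still mention would be exposed in the same way.

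The direction within groups is upward, placebo included, wherever there is uptake. With equal uptake and a common level in recipients, between-group ratios move toward 1. The 1.4- to 6.3-fold range shows what the assumed inputs imply; it is not an estimate for this trial.

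A reader might infer more than the document supports:
- that the 6-month results will certainly be contaminated, or are biased upward in every arm. Uptake is not given, so they can be, and it would go unseen;
- that infection data are also missing. Symptomatic COVID-19 is collected as an AESI;
- that the choice of formulations for Phase 2 is compromised. Day 29 and Day 43 precede the permission.

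**What to change.** 1. **Section 4.6 and the Table 3 footnotes:** record the date and product of any non-study COVID-19 vaccine through the last visit. Concomitant medication is already on the Visit 7 schedule, so this is one added question, or a retrospective query where the visit has passed.
2. **Section 6.3.5:** state that a subject's immunogenicity data leave the per protocol analysis from that date, whether or not the vaccination is a deviation. Apply the same rule to confirmed SARS-CoV-2 infection, using the AESI data already collected.
3. **Section 9 and the Day 197 tables:** report full analysis results with and without the affected samples, with the number affected by group. Table 7 can carry the per protocol exclusions.

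The cost is one data item and some SAP wording, plus a smaller, self-selected Day 197 per protocol set with wider intervals. For that reason neither version should be shown alone.
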